RB is computed by taking the numerical average and rounding to the nearest integer; RB does not require comparison to a historical ‘normal’.

10.4 Multiple Comparisons and Family-wise Type I Error Rate

All formal, controlled, pre-planned statistical analyses in this Protocol (primary endpoint and key secondary endpoints) are associated with Induction Week 13 – the end of the Induction Treatment Period.

[figure not shown]
Preservation of an overall 5% Type I error rate for the primary analysis of the primary endpoint and key secondary endpoints will rely on the primary analysis of the primary efficacy endpoint as a gatekeeper, followed by sequential application of a truncated Hochberg ([Dmitrienko 2008](#); [Dmitrienko 2011a](#); [Dmitrienko 2011b](#)) procedure (i.e., sequentially rejective method) to families of hypothesis tests. [Figure 3](#) illustrates the procedure.

The primary analysis of the primary efficacy endpoint will consist of an assessment of VTX002 60 mg versus Placebo for clinical remission at Induction Week 13. The null hypothesis associated with this analysis is denoted Family 1 and is a gatekeeper for the collection of Key Secondary Analyses comprised of hypothesis test families 2 through 6.

If this results in rejection of the null hypothesis at $\alpha = 0.05$, analysis proceeds to Family 2, consisting of null hypotheses for endoscopic improvement and symptomatic remission for VTX002 60 mg versus Placebo. If at least one of the hypotheses in this family is rejected in accordance with a truncated Hochberg procedure, some or all of the Type 1 error rate available for Family 2 is passed to Family 3 for additional hypothesis testing. If at least one of the hypotheses in Family 3 are rejected in accordance with a truncated Hochberg procedure, some or all of the Type 1 error rate available for Family 3 is passed to Family 4 – a gatekeeper hypothesis test assessing VTX002 30 mg versus Placebo with respect to the primary endpoint. This process continues until all hypothesis testing families (1 through 6) have been assessed or testing stops due to failure.

All other hypothesis tests (sensitivity analyses, supportive analyses, exploratory hypothesis tests) described in this SAP will be performed in an uncontrolled manner with nominal $\alpha = 0.05$, unless otherwise specified.

Figure 3. Sequentially Rejective Method: Truncated Hochberg Procedure

10.4.1 Hochberg Procedure

Consider testing the family of hypotheses $H_{0i}; i = 1 \dots k$. Let p_i , for $i = 1 \dots k$, denote the sample p -values of tests for $H_{0i}; i = 1 \dots k$, computed without multiplicity adjustment. Let $[1] \dots [k]$ denote the random indices such that $p[1] \leq \dots \leq p[k]$, such that $p[1]$ is the smallest p -value and $p[k]$ is the largest p -value. The Hochberg procedure is implemented as follows:

Step 1: if $p[k] < \alpha$, reject $H_{0[i]}, i=1, \dots, k$ and stop; otherwise proceed to next step.

Step 2: if $p[k-1] < \alpha/2$, reject $H_{0[i]}, i=1, \dots, (k-1)$, and stop; otherwise proceed to next step.

...

Step k : if $p[1] < \alpha/k$, reject $H_{0[1]}$, and stop; otherwise no null hypothesis is rejected.

10.4.2 Truncated Hochberg Procedure

Consider testing the family of hypotheses $H_{0i}; i = 1 \dots k$. Let p_i , for $i = 1 \dots k$, denote the sample p -values of tests for $H_{0i}; i = 1 \dots k$, computed without multiplicity adjustment. Let $[1] \dots [k]$ denote the random indices such that $p[1] \leq \dots \leq p[k]$, such that $p[1]$ is the smallest p -value and $p[k]$ is the largest p -value. The truncated Hochberg procedure employs a linear combination of a Bonferroni-adjusted significance level (α/k for all steps) with traditional Hochberg-adjusted significance levels (α at step 1, $\alpha/2$ at step 2, \dots , α/k at step k) at each step via a truncation fraction, $f \in [0, 1]$, and is implemented as follows:

Step 1: if $p[k] < f\alpha + (1-f)\alpha/k$, reject $H_{0[i]}, i = 1, \dots, k$ and stop; otherwise proceed to next step.

Step 2: if $p[k-1] < f\alpha/2 + (1-f)\alpha/k$, reject $H_{0[i]}, i = 1, \dots, k-1$, and stop; otherwise proceed to next step.

...

Step k : if $p[1] < f\alpha/k + (1-f)\alpha/k = \alpha/k$, reject $H_{0[1]}$, and stop; otherwise no null hypothesis is rejected.

A truncation fraction of $f=1$ yields a traditional Hochberg procedure, whereas a truncation fraction of $f=0$ yields a traditional Bonferroni procedure.

A truncation fraction of 0.7 will be applied in this study. Its application is demonstrated for Family 2 in Figure 3:

- At Step 1, the cutoff for the largest p -value is $0.7*(0.05) + 0.3*(0.025) = 0.035 + 0.0075 = 0.0425$.
 - Suppose the largest p -value is 0.04. Then both hypotheses are rejected and $\alpha=0.05$ is preserved and is passed in its entirety to Family 3 for use in hypothesis testing.

- Suppose the largest p-value is 0.045. Then the null hypothesis associated with this p-value is not rejected and we proceed to Step 2
- At Step 2, the cutoff for the next largest p-value is $0.7*(0.025) + 0.3*(0.025) = 0.025$
 - Suppose this p-value is 0.01. Then the hypothesis associated with this p-value is rejected and $\alpha_3 = \alpha_2 - [f\alpha_2 + (1-f)*\alpha_2/2] = 0.05 - [0.035 + 0.0075] = 0.0075$ is passed to Family 3 for use in further hypothesis testing.
 - Suppose this p-value is 0.03. Then the hypothesis associated with this p-value cannot be rejected and no Type 1 error rate may be passed to Family 3 (or any other hypothesis families) for additional controlled testing.

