9.7 Statistical Tests

The default statistical significance level will be 0.05 for two-sided hypothesis tests; one-sided hypothesis tests will not be performed unless explicitly stated otherwise. The default for confidence intervals (CIs) will be to generate two-sided 95% CIs.

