Table 6. Planned Primary and Key Secondary Analyses

X = VTX002 60 mg vs Placebo

Y = VTX002 30 mg vs Placebo

Endpoint	Primary Analysis with Stratified CMH (FAS)	Key Secondary Analyses with Stratified CMH ^b (FAS)	Section 16.1.4 Missing Data Sensitivity Analyses (FAS: MAR MI, CR MI, Tipping Point)	Section 16.1.5 Sensitivity Analysis (FAS)	Section 16.1.6 Supplementary Analyses (mFAS, PP Sets)	Section 16.1.7 Sensitivity Analyses (FAS)
Primary endpoint – Clinical Remission	X ^a Family 1	Y Family 4	X, Y	X	X, Y	X, Y
Key Secondary Endpoints						
Endoscopic Improvement		X: Family 2 Y: Family 5	X, Y		X, Y	X, Y
Symptomatic Remission		X: Family 2 Y: Family 5	X, Y		X, Y	X, Y
Histologic Remission		X: Family 3 Y: Family 6	X, Y		X, Y	X, Y
Endoscopic improvement – Histologic Remission		X: Family 3 Y: Family 6	X, Y		X, Y	X, Y

^a Serves as primary analysis gatekeeper for testing all Key Secondary Analyses with Stratified CMH

^b The collection of Key Secondary Analyses with Stratified CMH subject to a truncated Hochberg multiplicity adjustment to control the family-wise Type 1 error rate at $\alpha=0.05$. [Figure 3, Section 10.3](#) presents a flow chart demonstrating how this is to be done.

CMH = Cochran-Mantel-Haenszel; CR = copy reference; FAS = Full Analysis Set; mFAS = modified Full Analysis Set; PP = Per Protocol set; MI = multiple imputation; MAR = missing at random

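### On the readable SAP text, Family 6 (the last family) is also truncated at f = 0.7, although no later test can use the alpha held back; ordinary Hochberg there would be a small free gain, subject to checking Figure 3

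*SAP*

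**What the plan says.** SAP 10.4 tests six families in order, and alpha passes from each to the next. Table 6 assigns the hypotheses. Families 1 and 4 hold one each (clinical remission for 60 mg, then for 30 mg). Families 2, 3, 5 and 6 hold two each. The histologic pair is listed as "X: Family 3 Y: Family 6", where Y is 30 mg versus placebo.

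For the truncation fraction, SAP 10.4.2 states "A truncation fraction of 0.7 will be applied in this study". Footnote b to Table 6 describes "The collection of Key Secondary Analyses with Stratified CMH subject to a truncated Hochberg multiplicity adjustment" and excepts no family.

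On where the sequence ends, SAP 10.4 states "This process continues until all hypothesis testing families (1 through 6) have been assessed or testing stops due to failure". All other tests "described in this SAP will be performed in an uncontrolled manner with nominal" alpha of 0.05. No controlled test therefore follows Family 6.

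SAP 10.4.1 sets out the ordinary Hochberg test, and 10.4.2 notes that f = 1 reproduces it, but no readable text assigns it to a family. Figure 3, the flow chart to which the SAP refers for the procedure, is not shown in the text reviewed.

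**The concern.** Truncation is a trade. The first cutoff is lowered so that some alpha survives a partial rejection and can be passed on. Families 2, 3 and 5 need this, because without it one failed hypothesis in a pair would stop the sequence. In Families 1 and 4 the fraction has no effect, because a single hypothesis is tested at the full available alpha whatever f is.

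Family 6 makes the same payment but has no successor to receive the alpha. What is at stake is a little power for two controlled 30 mg claims. If testing reaches Family 6 with alpha 0.05 and the larger p-value is 0.045, the text as written denies that claim although control at 0.05 would allow it.

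**Working it through.** **Inputs.** Alpha is 0.05 two-sided (SAP 9.7: "The default statistical significance level will be 0.05 for two-sided hypothesis tests"). The fraction is f = 0.7 (SAP 10.4.2), and Family 6 has k = 2 hypotheses (Table 6). The documents give planning rates only for clinical remission on 60 mg and placebo (SAP 6), so the power inputs below are assumptions.

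**1. Reproducing the SAP's figures (alpha 0.05, k = 2, f = 0.7).**
- Step 1 cutoff = f·α + (1−f)·α/k: "0.7*(0.05) + 0.3*(0.025) = 0.035 + 0.0075 = 0.0425".
- Step 2 cutoff = f·α/2 + (1−f)·α/k = 0.0175 + 0.0075 = 0.025.
- Alpha passed on after one of two rejections: "0.05 - [0.035 + 0.0075] = 0.0075".

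All three agree with the SAP.

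**2. Cutoffs in Family 6.** With k = 2 and f = 0.7 the Step 1 cutoff is 0.7·α6 + 0.15·α6 = 0.85·α6. With f = 1 it is α6. The Step 2 cutoff is α6/2 in both cases.

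| Alpha reaching Family 6 | Step 1, f = 0.7 | Step 1, f = 1 | Step 2, either |
|---|---|---|---|
| 0.05 | 0.0425 | 0.05 | 0.025 |
| 0.0075 | 0.006375 | 0.0075 | 0.00375 |

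**3. Family-wise error with f = 1 in Family 6 only.**
- One true null in Family 6, everything else rejected: the error rate is 0.0425 with f = 0.7 and 0.05 with f = 1. The difference, 0.0075, is what the present text leaves unused.
- One true null in Family 5 and one in Family 6, everything else rejected: the Family 5 null is wrongly rejected with probability 0.0425. Otherwise only 0.0075 reaches Family 6. The total is at most 0.0425 + 0.0075 = 0.05.
- Simulating all six families over sampled null configurations gave the same maximum error rate for f = 0.7 and f = 1 in Family 6: 0.0506 with independent statistics and 0.0501 at correlation 0.5 (Monte Carlo standard error about 0.0005). A separate run of the mixed case above, with independent statistics, gave 0.0510 with f = 1. That is about two standard errors above 0.05, and the bound just shown caps the true value at 0.05.

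**4. Gain if Family 6 is reached with alpha 0.05.** Simulated from bivariate normal statistics; power is for each endpoint unadjusted.

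| Power per endpoint | Correlation | Both rejected, f = 0.7 | Both rejected, f = 1 | Gain (points) |
|---|---|---|---|---|
| 70% | 0.6 | 54.5% | 57.3% | 2.8 |
| 70% | 0.8 | 58.3% | 61.1% | 2.7 |
| 80% | 0.6 | 67.3% | 69.9% | 2.6 |
| 80% | 0.8 | 70.5% | 72.9% | 2.4 |

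(Gains are taken before rounding.) Widening the assumptions to 50-90% power and correlation 0-0.8 gives 1.7 to 3.4 points for both, 1.0 to 1.9 points per endpoint and 0.1 to 0.9 point for at least one.

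**5. Gain over the whole sequence.** Full alpha reaches Family 6 only if Families 1 and 4 are rejected and both hypotheses are rejected in each of Families 2, 3 and 5. With 80% power for all ten tests and a common correlation of 0.3-0.8, that happens in 30-57% of simulated trials. With 60 mg power of 80-95%, 30 mg power of 50-90% and no higher than that of 60 mg, and correlation 0.3-0.8, the chance of rejecting both Family 6 hypotheses rises by about 0.6 to 1.5 points. The gain can be smaller if 30 mg is assumed to have more power than 60 mg.

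**The case against.** The strongest objection is that Figure 3 carries the operative rule and is not shown. The prose of 10.4 names a truncated test explicitly only for Families 2 and 3, and the worked example is for Family 2. Section 10.4.1 sets out ordinary Hochberg separately, perhaps for the last family. This stands as a limit: a reader might infer that the SAP certainly applies 0.7 in Family 6, and the available text cannot settle that. The general wording of 10.4.2 and footnote b favours that reading. If the figure does use f = 1 for Family 6, those two places conflict with it and need the same sentence.

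Second, one fraction throughout is prespecified, simple and valid, and nothing obliges a plan to spend all its alpha in the last family. That also stands. A reader might infer a type I error problem; there is none, because the text errs on the conservative side.

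Third, a reader might take 2 to 3 points as the power lost by the trial. That figure is conditional on full alpha reaching Family 6, and over the whole sequence the gain is smaller. The power inputs have no source in the documents: the study is sized only for 60 mg clinical remission, and Protocol 4.4 chose the lower dose as one likely to sit low on the dose-efficacy curve.

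A last reservation is that Hochberg tests need positive dependence. The truncated version needs it too. Both Family 6 endpoints require a Geboes score below 2.0, and one is nested in the other, so the condition is plausible and nothing new is assumed.

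**Conclusion.** This is a free improvement of low severity, not an error. On the readable text, f = 0.7 applies to Family 6 with no exemption, and the 15% of its alpha held back from the Step 1 cutoff serves no later test. The effect is confined to that one cutoff for two 30 mg hypotheses. With full alpha it matters only when the larger p-value lies between 0.0425 and 0.05. Under the stated assumptions the gain in the chance of rejecting both is about 2 to 3 points if full alpha arrives, and about 0.6 to 1.5 points over the sequence. Confidence is limited by the missing Figure 3 and by the absence of 30 mg planning rates.

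**What to change.** Check Figure 3 first. Then add to SAP 10.4.2: *For Family 6, the last family, f = 1 (regular Hochberg, Section 10.4.1) is used; f = 0.7 applies to Families 2, 3 and 5.* Align Table 6 footnote b, and Figure 3 if it shows 0.7 for Family 6.

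The cost is one sentence, one footnote and possibly one figure. Sample size, data collection and Families 1 to 5 do not change, and family-wise error stays at 0.05. The change must be made before the interim database lock and unblinding, the point by which Protocol 9.4 requires the SAP to be final; made later, it could look data-driven.

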10.5 Subgroup Analyses

The primary and key secondary endpoints will be assessed for prespecified subgroups for the Induction Treatment Period (Induction Week 13). These subgroup analyses will be uncontrolled, are considered supportive, and will be based on the FAS. The following subgroups will be assessed:

- Randomization Stratification Factors – for these assessments, the stratification factor being assessed will be removed from any formal statistical tests
 - Biologic/JAK inhibitor prior use status (yes or no)
 - Number of prior biologic or JAK inhibitor therapies (1 or >1)
 - Prior UC treatment failure of anti-tumor necrosis factor alpha (anti-TNF α) (yes or no)
 - Baseline corticosteroid use (yes or no)
 - Baseline disease activity
 - MMS 5-6 or MMS 7-9
 - MMS 4-6 or MMS 7-9
- Other Factors
 - Sex (Female or Male)
 - Age (18-64, 65-74, 75-80, 18-44, 45-65, >65, ≥ 65 , ≥ 75)
 - Race (White or Non-White)
 - Region (North America, Western Europe, Eastern Europe, Other)
 - Baseline endoscopic subscore (2 or 3)
 - Baseline FCP (\leq or $>$ 250mg/kg)
 - Baseline high-sensitivity C-reactive protein (CRP) (\leq or $>$ 3mg/L)

- Baseline total Mayo score (TMS) (\leq or $>$ 8)
- Duration of UC at Screening (\leq or $>$ Median)
- Extent of disease at Screening (as collected in eCRFs)
 - Proctosigmoiditis
 - Pancolitis
 - Proctitis
- Prior UC treatment of oral 5-aminosalicylic acid (5-ASA) only (Yes or No)
- Prior UC treatment failure of oral 5-ASA only (Yes or No)

Additional subgroups may be assessed, if deemed necessary. The medians will be derived based on the FAS for all subgroups cut at the median. This study was not designed to detect treatment differences within subgroups. If a subgroup includes $<$ 10% of all participants, no inferential statistics will be generated.

The actual stratum at Baseline (as collected in EDC) will be used for all subgroup analyses, including randomization stratification factors. Randomization stratification factors not being treated as a subgroup for a particular subgroup analysis will also be handled according to actual Baseline stratum as collected in EDC.

Forest plots of the results associated not only with the overall FAS, but also all considered subgroups, will be presented for the primary endpoint and each key secondary analysis. Inference from the analyses described in [Sections 16.1.3](#) and [Section 16.2.1 Table 6](#), columns 2 and 3 will be used. Differences in responder percentages along with 95% CIs will be displayed. Sensitivity and/or Supplementary analyses will not be considered.

11. DISPOSITION AND PROTOCOL DEVIATIONS

11.1 Participant Disposition

All study participants providing informed consent will be accounted for in this study. Treatment for the Induction Treatment Period and LTE will be represented as-randomized. Treatment for OLE will be represented as-received. Percentages for participants will be based on the number of participants randomized in the Induction Treatment Period.

Participants screened and reason for screen fail will be summarized by number and percentage. Participants meeting all eligibility criteria but not randomized will be included in this summary as well. Inclusion criteria not met and exclusion criteria met will be included in this tabulation and will also be listed in participant listings.

Among study participants, disposition will be tabulated so that each protocol study period is separately represented (Induction Treatment Period, LTE, OLE). LTE and OLE are available

only for participants initially randomized into the Induction Treatment Period. Participant disposition tabulation for these study periods will display participant flow through all three study periods. A CONSORT diagram will also be developed.

There are three study period-specific completion status assignments a participant may have:

- A participant flagged with a status of “Treatment completed” on the End of Induction Treatment Period form is considered to be an Induction completer
- A participant flagged with a status of “Treatment completed” on the End of Long Term Extension Period form is considered to be an LTE completer
- A participant flagged with a status of “Treatment completed” on the End of Open Label Extension Period form is considered to be an OLE completer

Within a given study period, the number and percent of participants who completed/discontinued treatment, primary reason for discontinuation of treatment, the number and percent of participants who completed/discontinued the study period, and primary reason off study period will be summarized by number and percentage. This summary will also be provided by region and country. The number and percent of participants in each analysis set will be summarized.

Death is a reason for study discontinuation and will also be summarized for a given study period by number and percentage. The summary of death will include all SAEs with a fatal outcome.

Listings will be provided for participants’ study disposition, including reasons for exclusion and discontinuation from the study treatment, discontinuation from study periods and date/cause of death.

11.2 Protocol Deviations

After the last participant completes the Induction Treatment Period, the protocol deviation log for the Induction Treatment Period will be provided to Sponsor for review at the final Induction Treatment Period Blinded Data Review Meeting (BDRM). Sponsor will classify protocol deviations as either major or minor per the Protocol Deviation Plan (PDP).

Similarly, at the end of the study, the final project-level protocol deviation log will be provided to the sponsor prior to the final database lock. Upon the study end, the final project-level protocol deviation log will be approved by the sponsor at the final study BDRM and filed in trial master file (TMF).

For the Induction Treatment Period, major deviations will be separately summarized (number and percentage) by treatment group for the FAS according to the following categories, and all deviations will be listed:

- Withdrawal criteria
- Randomization procedure

- Subject visit completion or timing
- Study procedure or assessment
- Study medication
- (Serious) AE reporting
- Other

Note that participants experiencing an intercurrent event during the Induction Treatment Period and not experiencing other deviations preventing contribution to the primary and key secondary analyses of the primary and key secondary endpoints will be included in the PP set and treated as non-responders in those analyses.

A separate summary will be provided for protocol deviations occurring during the entire study. The FAS-ET set and planned treatment group will be used for this purpose.

12. DEMOGRAPHIC AND BASELINE CHARACTERISTICS

The following demographic variables will be summarized, as collected in EDC:

- Baseline Age (yr)
- Baseline Age Group (18-<65 ≥65)
- Baseline Height (cm)
- Baseline Weight (kg)
- BMI (kg/m²), derived from Screening weight (kg) and height (m)
- Baseline eGFR (mL/min/1.73m²), derived from serum creatinine using the 2021 update to the CKD-EPI formula
- Country
- Sex (M/F)
- Female of Childbearing potential (Y/N)
If No:
 - Surgical Sterilization or Hysterectomy (Y/N)
 - Post-menopausal for more than 1 year (Y/N)
- Ethnicity
- Race

Separately, Baseline¹ UC signs and symptoms will be presented, where Baseline is understood to be the most recently available measurement prior to administration of study treatment. For these UC Baseline signs and symptoms, stool frequency and rectal bleeding data derived from eDiary will be presented, as opposed to what is available from EDC. Refer to [Section 10.3](#) for a description of how eDiary data is processed to determine the stool frequency and rectal bleeding subscores. Derived stool frequency and rectal bleeding data will also be used for efficacy endpoint evaluation, and if these values are present in EDC but not calculable from eDiary, they will be treated as missing. The following UC Baseline signs and symptoms will be summarized descriptively:

- Duration of Ulcerative Colitis (yr): (Informed consent date – Date of diagnosis + 1) / 365.25
- Location and extent of Ulcerative Colitis (Proctosigmoiditis, Pancolitis, Proctitis, Other)
- Any surgeries related to Ulcerative Colitis? (Y/N)
If Yes:
 - Number of surgeries
- Colonoscopy within past 12 months? (Y/N)
- Endoscopic Score (ES)
- Stool Frequency (SF)
- Rectal Bleeding (RB)
- Physician’s Global Assessment (PGA)
- Mayo Clinic Score (MCS)
- Modified Mayo Score (MMS)
 - MMS Group (5-6, 7-9)
 - As collected in IWRS
 - As collected in EDC
- Partial Mayo Score (PMS)
- Stable corticosteroids (Y/N)
 - As collected in IWRS
 - As collected in EDC

¹ Baseline refers to the most recently available measurement(s) prior to administration of study treatment. For some UC signs and symptoms, such as Endoscopic Score, this is strictly a Screening data point. For others such as Physician’s Global Assessment (PGA) and MCS (which uses PGA as a component), these are Study Day 1 pre-dosing values.

- Prior biologic/JAK (Y/N)
 - As collected in IWRS
 - As collected in EDC
 - Prior failure of anti-TNF (Y/N) as collected in EDC
 - Prior failure of vedolizumab (Y/N) as collected in EDC
 - Prior failure of both anti-TNF and vedolizumab (Y/N) as collected in EDC
 - Prior failure of JAK inhibitor (Y/N) as collected in EDC
- Prior failure of oral 5-ASA only (Y/N) as collected in EDC

For the Induction Period Analysis, summaries will be presented by planned treatment group and overall for the FAS, mFAS, and PP populations. At study end, summaries will be presented by planned treatment group and overall for FAS-ET population. Listings will be provided for all demographic and baseline variables, and derived SF and RB values will be presented along with SF and RB as collected in EDC, and in this listing differences between EDC and programmatically-derived SF and RB scores will be flagged.

